### **Double-Blinded Treatment Period (DTBP)**

For each cohort:

The dosing of IMP will begin at V1 and continue throughout the DBTP.

[figure not shown]
- The DBTP will begin 7 days after the final IVIg administration of the IVMP

- Participants will be randomized at day 1 of the DBTP (Figure 1):
  - [REDACTED]
  - [REDACTED]
  - [REDACTED]
  - [REDACTED]
  - Randomization will be stratified based on an individual's IVIg dose frequency as described in Section 2.2.
- For cohort 2, the dose regimen chosen by the EDRT will remain blinded to the participant, investigator, and the sponsor's study team to avoid any bias in the outcome assessments.
- Participants will be treated with IVIg during the DBTP if there is a clinically meaningful deterioration in muscle strength and/or motor function. [REDACTED]  
[REDACTED]  
[REDACTED]
  - Administration of IMP will not be paused/stopped when IVIg retreatment is initiated
  - Based on their clinical judgment, the investigator may choose to not re-treat the participant with IVIg in the event of a clinically meaningful deterioration
  - All study participants can request IVIg retreatment with the investigator anytime during the DBTP.

The following interim database locks will occur:

- After the completion of the 16-week DBTP by all participants included in cohort 1. Only participants from cohort 1 will be unblinded
- After the completion of the 16-week DBTP by the 24th participant included in cohort 2. The second interim analysis will include all participants included in cohort 2 and all participants of cohort 2 will be unblinded, even ongoing participants.

A final database lock will occur when all participants have completed the safety follow-up period, or have rolled over to the long-term extension (LTE) study, if applicable.

[figure not shown]

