## 2.4 Blinding

This is a double-blinded trial in which the investigator, study nurse/coordinator, participant, the sponsor's designated contract research organization (CRO), and sponsor study team are blinded to study intervention during the entire DBTP even if the participant withdraws from the study or enters the LTE.

For the conduct, analysis and monitoring of the trial, some study staff are unblinded to treatment assignment:

- clinical study pharmacy staff, due to the difference of viscosity between placebo and ARGX-117
- an unblinded clinical study supply manager
- an unblinded Clinical Research Associate who will monitor pharmacy
- an unblinded data manager who will have access to unblinded data (eg, PK) for data cleaning reconciliation
- an unblinded independent statistician from IRT vendor who will prepare and have access to the randomization code

Although unblinded to treatment assignment, none of the above roles will have access to unblinded summaries of efficacy or safety data.

The IDMC will have access to unblinded safety and efficacy data reports to discharge their roles for data analysis and review during IDMC meetings. These reports will be prepared by the unblinded independent IDMC support statistician.

The unblinded EDRT, composed of senior executive members from the sponsor, will have access to unblinded data for the purpose of strategical decision making and planning.

[REDACTED]

[REDACTED]  
[REDACTED]  
[REDACTED]  
[REDACTED]

[REDACTED]

- [REDACTED]  
[REDACTED]
- [REDACTED] [REDACTED]  
[REDACTED]  
[REDACTED]

[REDACTED]  
[REDACTED]  
[REDACTED]  
[REDACTED]  
[REDACTED]  
[REDACTED]  
[REDACTED]

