### 4.2 Protocol Deviations

Protocol deviations will be classified during monthly meeting as non important or important based on their effect on the rights, safety, or wellbeing of the participants and/or the quality and integrity of the data. The final rating will be confirmed on a blinded case-by-case basis prior to database lock (DBL).

Summaries of protocol deviations will be provided by class of deviation, overall and by treatment group in the SAF.

All protocol deviations will be listed.

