**Double Blind Treatment Period (DBTP):**

- For the efficacy endpoints: From the first IMP administration date/time to V14 with 23:59 added as time part or date of early treatment discontinuation visit with 23:59 added as time part
- For AE and concomitant medication: From the first IMP administration date/time to:
  - Informed consent of LTE for participants who do enter into LTE. Date of informed consent corresponds to the treatment completion date in the main study. All data on the eCRF will be considered to belong to this period
  - 23h59 the day prior to the 1st FU visit at week 4 for those participants who do not enter into LTE or date of early study discontinuation with 23:59 added as time part if participant discontinued the study before FUV1
  - Date of study discontinuation with 23:59 added for participants who early discontinued study and do not enter in the safety follow up period

**DBTP and Safety Follow-up period:** For AE, from the first IMP administration date/time to:

- Informed consent of LTE for participants who do enter into LTE. Date of informed consent corresponds to the treatment completion/discontinuation date. All data on the eCRF will be considered to belong to this period
- Study discontinuation for those participants who do not enter into LTE

Participants who entered into LTE are participants who were eligible for LTE and signed the informed consent form.

**Study Day 1 IDVP:** The day of the first IVIg administration during IDVP

**Study Day 1 IVMP:** The day of the first IVIg administration during IVMP

**Study Day 1:** The day of the first administration of ARGX-117 or placebo

**Study Day 1 FU:** The day following V14/ED visit (D113) (for participants who do not enter into the LTE)

**End of Treatment Visit:** The V14 visit (D113) for participants who completed DBTP, or the visit following IMP discontinuation for participants who discontinue IMP prior to V14 (D113) or the last IMP administration date for participants who are on-going in the DBTP at the data cut-off date .

**End of Study Visit:** The V14 visit (D113) for participants entering the LTE, or the last recorded date in the DBTP or SFU period for participants not entering the LTE.

Scheduled or Unscheduled visits which do not fall into the visit windows will be listed, but not included in tables or graphs.

- **Conversion factors:**
  - 1 month = 30.4375 days
  - 1 year = 365.25 days
  - 1 week = 7 days
  - °C = (°F - 32)/1.8
- **Additional rules**

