### 6.5 Efficacy Evaluation

#### 6.5.1 Efficacy of ARGX-117 compared to placebo on muscle strength and/or motor function in adult participants previously stabilized with IVIg

##### 6.5.1.1 Retreatment with IVIg

Summary data will be presented by treatment group. This analysis will be performed in the SAF set only.

- Time to the first retreatment with IVIg since the final IVIg treatment of the IVMP

Time to first retreatment with IVIg is defined as the time from last IVIg administration before randomization (including unscheduled visits) up to the first IVIg retreatment during DBTP.

*Time to first retreatment with IVIg = (start date of first IVIg retreatment during DBTP – stop date of last IVIg treatment before randomization)*

For participants who are not retreated with IVIg during the DBTP this will be calculated as:

*Time to first retreatment with IVIg = censoring date – stop date of last IVIg treatment before randomization*

If the stop date of last IVIg treatment before randomization is missing then the start date will be used.

The censoring date will be determined as follows:

- If the participant completes DBTP, the censoring date will be the date of last visit V14 (D113)
- If the participant early discontinues treatment, the censoring date will be the date of early discontinuation of treatment
- If the participant is ongoing in cohort 2, the censoring date will be the date of the data cutoff date

Participants who are lost to follow-up in the DBTP will be censored at the date of last visit available.

Time-to-event variables will be descriptively presented with median times, quantiles, and number and percentage of participants censored and with event (KM estimates). The probability of participants being retreated will be displayed by treatment group in the form of cumulative probability curves estimated using the non parametric Kaplan-Meier method. The CI for the median will be calculated using the Brookmeyer and Crowley method.

[REDACTED]

[REDACTED]

[REDACTED]

[REDACTED]

[REDACTED]

[REDACTED]

[REDACTED]

[REDACTED]

[REDACTED]

[REDACTED]

[REDACTED]

[REDACTED]

[REDACTED]

[REDACTED]

[REDACTED]

[REDACTED]

[REDACTED]

[REDACTED]

Time to IVIg retreatment will be listed.

- Time to relapse

Time to relapse is defined as the time from randomization up to the time participant meets threshold for clinical deterioration.

For a participant, the threshold for relapse status is met if one of these criteria is established:

[REDACTED]

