## 7 CHANGES TO PLANNED ANALYSES

The changes between the protocol-defined statistical analyses and those presented in this statistical analysis plan are the following:

[REDACTED]  
[REDACTED]  
[REDACTED] All participants from cohort 2 will be included in the analysis (even ongoing participants) and will be unblinded.

The following endpoints were added:

[REDACTED]  
■ [REDACTED]  
■ [REDACTED]  
■ [REDACTED]  
■ [REDACTED]  
■ [REDACTED]

[REDACTED]  
■ [REDACTED]  
■ [REDACTED]  
[REDACTED]

[REDACTED]  
■ [REDACTED]

[REDACTED]  
■ [REDACTED]

[REDACTED]  
■ [REDACTED]  
■ [REDACTED]  
■ [REDACTED]  
[REDACTED]

[REDACTED]  
■ [REDACTED]  
■ [REDACTED]  
■ [REDACTED]  
■ [REDACTED]  
[REDACTED]

- [REDACTED]

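### The interim 2 rule unblinds cohort 2 participants still in the double-blind period, conflicts with the readable blinding rule, and leaves their later data unseparated in the final analysis

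*SAP*

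**What the plan says.** SAP Section 2.1 (Double-Blinded Treatment Period) sets two interim database locks. The first waits until every cohort 1 participant has finished the 16-week DBTP. The second is triggered when the 24th cohort 2 participant finishes it, takes in all of cohort 2, and states that "all participants of cohort 2 will be unblinded, even ongoing participants". Section 7 lists this among the changes from the protocol: "All participants from cohort 2 will be included in the analysis (even ongoing participants) and will be unblinded".

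Other sections show that ongoing means still on double-blind treatment. Section 5.2 defines the end-of-treatment visit as "the last IMP administration date for participants who are on-going in the DBTP at the data cut-off date". Section 6.5.1.1 adds a censoring rule: "If the participant is ongoing in cohort 2, the censoring date will be the date of the data cutoff date".

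Section 2.4 says that the investigator, the nurse or coordinator, the participant, the CRO and the sponsor's study team "are blinded to study intervention during the entire DBTP even if the participant withdraws from the study or enters the LTE". It gives unblinded data to the IDMC, its independent support statistician and the EDRT, and lists some operational unblinded roles such as pharmacy staff. The readable part contains no exception for interim 2.

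Section 4.2 has deviation ratings confirmed blind before database lock. It does not say which lock.

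**The concern.** A participant who is mid-DBTP at interim 2 cannot be both unblinded and covered by a rule that keeps the site, the participant and the study team blinded to the end of the DBTP, unless the recipients of the code are restricted. Neither Section 2.1 nor Section 7 states a restriction in its readable text.

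The endpoints leave room for judgement. Under Section 2.1 the investigator may decline to retreat after a deterioration, and any participant may ask for IVIg at any time. Time to first retreatment is the first secondary efficacy endpoint in Section 3.2. Retreatment also fixes the derived visit in Section 6.2.1.2 that takes the last value before retreatment, used for mMRC, grip strength, MMN-RODS, CAP-PRI, FSS and PGIC. One altered decision would therefore touch several endpoints. Section 2.1 itself gives avoidance of bias in outcome assessment as the reason for masking the cohort 2 regimen.

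Section 5.3 and Table 24 carry cohort 2 into the final analysis. No readable text flags or removes observations made after the codes were opened.

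**Working it through.** **1. The plan's own figure.** Section 6.1 plans 48 participants, 16 per arm. Section 2.2 gives 24 per cohort, allocated 2:1 in cohort 1 and in options 1 and 2 of cohort 2. Active: 24 × 2/3 = 16 per cohort. Placebo: 24 × 1/3 = 8 per cohort, 16 pooled. Total 16 + 16 + 16 = 48, as stated. Under option 3 (2:2:1:1) cohort 2 splits 8/8/4/4, which is again 8 on placebo.

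**2. Can anyone be ongoing?** Section 2.2 says 24 per cohort, but Section 2.1 says at least 24. The end-of-treatment and censoring rules quoted above exist only for participants who are ongoing at the cut-off, so the SAP foresees some. It gives no number.

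**3. Share of cohort 2 affected (assumption).** Suppose cohort 2 randomises 24 + k and those k are in the DBTP at interim 2. The share is k/(24 + k).

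| k | Share |
|---|---|
| 0 | 0% |
| 1 | 1/25 = 4.0% |
| 2 | 2/26 = 7.7% |
| 4 | 4/28 = 14.3% |
| 6 | 6/30 = 20.0% |

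**4. Time left.** From Day 1 to V14 (Day 113) is 112 days. If the trigger participant is also the 24th randomised, someone randomised d days later has about d days left at the trigger: d = 28 gives 28/112 = 25%, d = 56 gives 50%, d = 84 gives 75%. Any delay between trigger and unblinding shortens this.

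**5. Weight of one decision.** For k = 2 to 6, cohort 2 placebo numbers about 26/3 = 8.7 (say 9) to 30/3 = 10. One changed retreatment decision moves that proportion by 1/9 = 11.1 to 1/10 = 10.0 percentage points. This requires that the participant is on placebo, has not yet been retreated, and is handled by someone who knows the arm.

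**6. Type of harm.** Sections 2.1 and 6.1 rule out formal hypothesis testing and give no alpha, power or effect size. No error rate can be computed. What can go wrong is the estimates.

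**The case against.** The strongest reply is that the texts can be read together. Section 2.1 speaks of database locks and does not say to whom the codes are released, and nothing readable says that sites, participants or assessors are told. If the codes serve the analysis only and sites stay masked, retreatment decisions and patient-reported scores are largely protected. The text after Section 2.4 is blacked out, and the contents list places Section 2.5, Interim Analyses, there. The lines before the quoted sentence in Section 7 are blacked out too. A firewall may be written in either place.

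This stands as a limit on the bias claim. A reader might infer that sites and participants are unblinded, or that the plan places no limit on recipients; the documents support neither inference. It does not remove the conflict, because the sentences in Sections 2.1 and 7 carry no qualifier and Section 2.4's readable text has no exception.

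A second reply is that ongoing participants are already censored at the cut-off, and Table 24 schedules the same efficacy tables at interim 2 and at the end. The interim output is thus close to an analysis without later data. That holds in part, and it makes a sensitivity analysis cheap. But the censoring rule acts at the interim only, the cut-off and the unblinding date need not coincide, and the final analysis does not refer back to it.

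A reader might also infer from Section 4.2 that blinded deviation rating has become impossible. It has not. The section says database lock, not final lock, Section 2.1 calls the interims database locks, and deviation outputs are scheduled at them (Listing 16.2.2.1 at interim 1, Table 14.1.6 at interim 2). Rating before each cohort's unblinding is a natural reading.

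**Conclusion.** The conflict between Sections 2.1 and 7 on one side and Section 2.4 on the other is real on the readable text and should be resolved. The bias is conditional: it arises only if the codes of ongoing participants reach people who can influence retreatment or ratings, which the redacted text may prevent. If they do, later data from those participants enter the final analysis with no readable rule to set them apart.

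The size is undetermined. The affected share of cohort 2 is 0% if nobody is ongoing, and 7.7% to 20% under the assumption of 2 to 6 participants beyond 24. One changed decision would then be worth about 10 to 11 points in the cohort 2 placebo arm. Section 6.2.1.2 compares each active group with the placebo group of its own cohort, so this small arm matters. It would be wrong to infer an inflated type I error, since no test is planned. Interim 1 raises no such problem, because all cohort 1 participants have finished the DBTP by then.

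**What to change.** **Blinding.** In Sections 2.1 and 7, with a cross-reference in 2.4, state that at interim 2 the individual codes of participants still in the DBTP go only to the independent IDMC support statistician, the IDMC and the EDRT. State that sites, participants, assessors, the CRO and the study team stay blinded until each participant's V14 or early discontinuation visit. If redacted text already says this, a cross-reference is enough.

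**Final analysis.** Add a sensitivity analysis that cuts the efficacy data of participants ongoing at interim 2 at the unblinding date.

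**Section 4.2.** Say that ratings are confirmed before the interim lock at which the cohort concerned is unblinded. For participants still ongoing, later deviations can then be rated while their codes remain closed to the raters.

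If interim 2 has already been run (the version 3.0 history entry about quantification limits missing for interim 2 suggests so), record who held which codes and when, and keep the sensitivity analysis.

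**Cost.** SAP wording, a release rule for the randomisation codes and one extra run. The small downside is that ongoing participants drop out of unblinded subject-level output at interim 2. That includes the individual-value PK tables 14.2.2.2 and 14.2.2.3, where appearing at all reveals active treatment because the PK set excludes placebo.

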### Safety Follow-up Period

After completing the 16-week DBTP, participants may enroll in an LTE study (which is not part of ARGX-117-2002) and continue to receive ARGX-117; otherwise, participants will enter the safety follow-up (SFU) period (without ARGX-117 treatment). The safety follow-up period will characterize safety, PK, and PD during the elimination of ARGX-117. The SFU period will begin after the DBTP and will continue for at least 15 months; the day of the first SFU visit will be considered the start of the SFU period.

A schematic of the study design is shown in [Figure 2](#). The schedule of activities is in appendix 9.1, further details are available in the study protocol.

## Figure 2 Study Design

EDRT=executive data review team; IDMC= independent data monitoring committee; IVIg=intravenous immunoglobulin; MCC=MMN confirmation committee; MMN=multifocal motor neuropathy

Note: An IVIg cycle is 1 administration of IVIg.

[REDACTED]

[REDACTED]

[REDACTED]

## Sample Size and Power

This is an exploratory study, no formal sample size calculation was made, and no formal hypothesis testing will be performed. A total of 48 participants (16 per treatment arm) are planned to be randomized, which is considered sufficient to respond to the primary objective (refer to Section 6.1).

## 2.2 Randomization Methodology

In this randomized controlled trial, for each cohort, 24 participants will be randomized using an interactive voice/web response system (IVRS/IWRS).

Participants will be randomized on day 1 of the DBTP:

- In a 2:1 ratio to ARGX-117 or placebo in cohort 1, and for option 1 ( ) or option 2 ( ) in cohort 2
- In a 2:2:1:1 ratio to ARGX-117 ( ) ARGX-117 ( ) placebo ( ) , or placebo ( ) for option 3 in cohort 2

Participants will be randomized on day 1 of the DBTP: ( )

## 2.3 Stopping Rules

The trial shall be immediately suspended, and an urgent referral made to the IDMC for expedited advice if the stopping rules described in the protocol v4.0 are met.

## 2.4 Blinding

This is a double-blinded trial in which the investigator, study nurse/coordinator, participant, the sponsor's designated contract research organization (CRO), and sponsor study team are blinded to study intervention during the entire DBTP even if the participant withdraws from the study or enters the LTE.

For the conduct, analysis and monitoring of the trial, some study staff are unblinded to treatment assignment:

- clinical study pharmacy staff, due to the difference of viscosity between placebo and ARGX-117
- an unblinded clinical study supply manager
- an unblinded Clinical Research Associate who will monitor pharmacy
- an unblinded data manager who will have access to unblinded data (eg, PK) for data cleaning reconciliation
- an unblinded independent statistician from IRT vendor who will prepare and have access to the randomization code

Although unblinded to treatment assignment, none of the above roles will have access to unblinded summaries of efficacy or safety data.

The IDMC will have access to unblinded safety and efficacy data reports to discharge their roles for data analysis and review during IDMC meetings. These reports will be prepared by the unblinded independent IDMC support statistician.

The unblinded EDRT, composed of senior executive members from the sponsor, will have access to unblinded data for the purpose of strategical decision making and planning.

[REDACTED]

[REDACTED]  
[REDACTED]  
[REDACTED]  
[REDACTED]

[REDACTED]

- [REDACTED]  
[REDACTED]
- [REDACTED] [REDACTED]  
[REDACTED]  
[REDACTED]

[REDACTED]  
[REDACTED]  
[REDACTED]  
[REDACTED]  
[REDACTED]  
[REDACTED]  
[REDACTED]

### 3 STUDY ENDPOINTS

#### 3.1 Primary Endpoints

Safety variables include AEs, clinical laboratory variables, vital signs and suicidal behavior.

#### 3.2 Secondary Efficacy Endpoints

- **IVIg retreatment**
  - Time to the first retreatment with IVIg since the final IVIg treatment of the IVMP
  - Time to relapse
  - Number of participants retreated with IVIg
  - Number of IVIg administrations during DBTP
  - Total IVIg dose (g/kg)
  - Average IVIg dose / week (g/kg)
  - Average IVIg dose interval (weeks)
- **Endpoints derived from modified Medical Research Council (mMRC) scores:**
  - **mMRC-10 sum score**
    - Value and change from baseline in mMRC-10 sum score
    - Net incremental Area Under the Curve (iAUC) per week of the change from baseline in mMRC-10 sum score
    - Proportion of participants showing a deterioration of at least 2 points as assessed by the mMRC-10 sum score
- **mMRC-14 sum score**
  - Value and change from baseline of mMRC-14 sum score
  - Value and change from baseline in the average of the mMRC-14 sum score for the 2 most important muscle groups
- **Endpoints derived from GS:**

For each hand (the most affected and the less affected hand):

  - Value, change from baseline, percent change from baseline and maximal percent change from baseline of GS daily average
  - Net iAUC per week of the change from baseline of GS daily average
  - Value, change from baseline, percent change from baseline of GS 3-day moving average
  - Proportion of participants with > 30% reduction from baseline over 2 consecutive days of GS 3-day moving average
- **Endpoints to assess functional ability, arm and hand function, quality of life, and fatigue**
  - **MMN-RODS**
    - Values and change from baseline in MMN-RODS centile metric score
    - Values and change from baseline in MMN-RODS raw score

- 9 Hole Peg Test (9-HPT)
  - For each hand (dominant / non dominant)
    - Values, change from baseline and percent change from baseline in average time (seconds)
- EQ-5D-5L
  - For each dimension (Mobility, Self-care, Usual activities, Pain/Discomfort, Anxiety/Depression):
    - Proportion of participants by level of severity
  - For the health state VAS:
    - Value and change from baseline
- CAP-PRI
  - Values and change from baseline in CAP-PRI total score
- Patients' Global Impression of Change (PGIC)
  - Proportion of participants by level of improvement
- Fatigue Severity Scale (FSS)
  - Values and change from baseline in the FSS total score
- **Endpoints to assess health-related productivity and work productivity**
  - Health-Related Productivity Questionnaire (HRQP)
    - Value at each visit:
      - Hours lost due to absenteeism
      - Hours lost due to presenteeism
      - Total hours lost (absenteeism and presenteeism)
      - Percent of scheduled hours lost due to absenteeism
      - Percent of scheduled hours lost due to presenteeism
      - Percent of total scheduled hours lost (due to absenteeism and presenteeism)

These endpoints will be derived for work-related activities and household chores activities.
- **Endpoints to assess medication treatment satisfaction**
  - Treatment Satisfaction 14-Item Questionnaire for Medication (TSQM-14)
    - For each subscale (Effectiveness, Side effects, Convenience, Overall Satisfaction)
      - Value at each visit of the subscale score
- **Endpoints to assess PK, PD and immunogenicity**

Serum concentrations and PK parameters for ARGX-117:  $AUC_{0-t}$ ,  $AUC_{72h}$ ,  $AUC_{0-168h}$ ,  $AUC_{336h}$ ,  $AUC_{\infty}$ ,  $C_{max}$ ,  $C_{72h}$ ,  $C_{168h}$ ,  $T_{max}$ ,  $t_{1/2}$ ,  $V_z$  and CL

Values, change from baseline and percent change from baseline, maximum percent change from baseline, maximum decrease from baseline (applicable for free C2 and CH50 only), minimum post baseline value (applicable for free C2 and CH50 only), maximum increase from baseline, maximum post baseline value (applicable for Total C2 only) in free C2, total C2, functional complement activity (CH50) over time

- Incidence and prevalence of antidrug antibodies (ADA) against ARGX-117

[REDACTED]

- [REDACTED]  
[REDACTED]
- [REDACTED]

